8.1 Inclusion criteria

- Adults (≥16 years) with altered consciousness level AND/OR behavioural change AND/OR working memory deficit AND/OR psychiatric symptoms
- Persisting for >24 hours and <3 months
- In whom clinician thinks autoimmune encephalitis is the most likely diagnosis
- CSF polymerase chain reaction (PCR) negative for HSV 1 and 2, and varicella zoster virus
- CSF microscopy and culture negative at 48 hours for organisms

PLUS 2 or more of:

- Seizures (not explained by previously known seizure disorder) OR new movement disorder
- Cerebrospinal fluid (CSF) white blood cell count 6-1000/mm3
- Electroencephalogram consistent with encephalitis
- Brain magnetic resonance imaging (MRI) or computer tomography (CT) changes consistent with encephalitis

8.2 Exclusion criteria

The patient is not eligible for the trial if any of the following apply:

- No other likely diagnosis
- Current or recent (within last 6 months) treatment with IVIG
- Contraindication to IVIG
- Intolerance of corticosteroids
- Recent history of gastric ulcers

- CSF analysis not performed
- CSF polymerase chain reaction (PCR) positive for any viruses
- Brain imaging not performed
- Alternative diagnosis on brain imaging (CT or MRI)
- Known HIV infection
- On steroids or other disease modifying anti-inflammatory therapies
- Not able to live independently prior to onset of condition

9 Recruitment, Screening and registration

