- A set of laboratory normal ranges and laboratory certification/accreditation from the host care organisation laboratory being used for analyses
- Pharmacy confirmation that they have received the first shipment of IMP prior to opening the site. N.B. This is not a regulatory requirement more good practice.
- Executed MTA for studies that had a translational component
- Returned Source Data Agreement signed by the PI

Upon receipt of all the above documents, the Trial Manager will send written confirmation to the Principal Investigator detailing that the centre is now ready to recruit participants into the trial. This email must be filed in each site's Site File. Along with the written confirmation, the site should receive their trial drug supplies and a trial pack holding all the documents required to recruit into the Trial.

Occasionally during the trial, amendments may be made to the trial documentation listed above. CTR will issue the site with the latest version of the documents as soon as they become available. It is the responsibility of the CTR to ensure that they obtain local R&D approval for the new documents.

Site initiation will be by conducted either in person or by tele/video conference.

8 Participant selection

Participants are eligible for the trial if they meet all the following inclusion criteria and none of the exclusion criteria apply. All queries about participant eligibility should be directed to the Trial Manager before randomisation/registration.

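### An exclusion criterion is worded the wrong way round: read literally, having no competing diagnosis makes a patient ineligible

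*Protocol*

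**What the plan says.** The lead-in to Section 8 sets the rule: "Participants are eligible for the trial if they meet all the following inclusion criteria and none of the exclusion criteria apply". Section 8.2 then opens its list with "The patient is not eligible for the trial if any of the following apply", and the first bullet is "No other likely diagnosis". The synopsis puts the same line first under its exclusion criteria.

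Two other items bear on the meaning. Section 8.1 describes the target patient as one "In whom clinician thinks autoimmune encephalitis is the most likely diagnosis". Further down the Section 8.2 list is "Alternative diagnosis on brain imaging (CT or MRI"), which excludes a patient because a competing explanation has been found.

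Nothing elsewhere in the protocol reverses or qualifies the first bullet, and the amendment history does not mention it.

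**The concern.** The bullet is a condition that the trial wants to be true of its participants, placed in a list of conditions that bar entry. Eligibility text is binding, so a clinician who follows it exactly turns away the clearest cases of autoimmune encephalitis. A clinician who enrols such a patient has to disregard a written exclusion to do so.

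What is at stake is the definition of the study population. Section 16.7 already names a pragmatic definition of the disease at entry as one of the factors that may limit the trial's ability to determine efficacy. The rule on competing diagnoses belongs to that definition. If it is unclear, sites have to settle for themselves whether a patient with a second likely diagnosis may enter.

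**Working it through.** No arithmetic applies. The check is to apply the Section 8 rule as written: a patient is eligible when every inclusion statement is true and every exclusion statement is false.

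**Could this be a text-extraction fault?** No. The line stands in two separate places, the synopsis and Section 8.2, each time within the exclusion criteria.

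**Could the list follow a convention that rescues the line?** No. Other negatively worded bullets work correctly when taken literally. For example, "CSF analysis not performed" excludes a patient when the negative state is true, as it should. The bullets on brain imaging not having been done and on inability to live independently beforehand behave the same way. Under that convention, the first bullet excludes a patient when it is true that there is no other likely diagnosis.

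**What does each reading do?** Suppose all other criteria are met and consider four kinds of patient under three readings of the line: taken literally, ignored as a slip, or reversed to mean *another likely diagnosis*.

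| Patient | Literal | Ignored | Reversed |
|---|---|---|---|
| A. Autoimmune encephalitis most likely, nothing else likely | Excluded | Admitted | Admitted |
| B. Autoimmune encephalitis most likely, another diagnosis also likely but not seen on imaging | Admitted | Admitted | Excluded |
| C. As B, but the other diagnosis is seen on imaging | Excluded | Excluded | Excluded |
| D. Autoimmune encephalitis not the most likely diagnosis | Excluded | Excluded | Excluded |

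Row A shows the inversion: the intended patient is barred only under the literal reading. Rows C and D do not depend on the line, because the imaging exclusion and the Section 8.1 inclusion item decide them.

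Row B shows what remains once the slip is recognised. The words *most likely* in Section 8.1 leave room for a second diagnosis that is likely but less so. Ignoring the line admits that patient and reversing it excludes that patient. Both are sensible ways to work around the error, and they define different populations.

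**The case against.** The best reply is that nobody will follow the literal reading. It makes no sense in a trial of patients thought to have autoimmune encephalitis, and the same list excludes an alternative diagnosis on imaging and any positive viral PCR. A delegated clinician confirms eligibility (Section 9.1), and queries go to the Trial Manager before randomisation (Section 8). Monthly screening logs (Section 9.2) should also show up a site that was turning patients away on this item. Even if the line were ignored, Section 8.1 still requires autoimmune encephalitis to be the leading diagnosis, negative PCR for herpes simplex and varicella zoster, negative microscopy and culture, and at least two supporting features. Much of this stands. The intended direction is fairly plain, and the room for harm is bounded.

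It does not dispose of the point. Knowing that the line is wrong does not tell a site whether to drop it or reverse it, and row B turns on that choice.

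A reader might go further and infer that the trial will in practice screen out its target population, because sites tick through the criteria one at a time on the database. The documents do not support this. Sections 9.1 and 9.4.1 and Figure 5 in Section 18 say only that a clinician confirms eligibility and that it is recorded electronically. The form's structure and wording are not shown. Nor do the documents show that the treatment effect will be diluted, that populations will differ between sites, or that correct enrolments will be logged as breaches. Each of these depends on how sites read the line.

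**Conclusion.** The point holds as a polarity error in binding eligibility text, present in both places where the criterion appears. As written, the rule excludes patients whose only likely diagnosis is autoimmune encephalitis and passes those with a competing likely diagnosis not seen on imaging. It does not exclude everyone, since the patients in row B would still qualify.

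Its practical size cannot be stated. That would need the proportion of screened patients who have a second likely diagnosis, and the way each of the 50 planned sites reads the line; the protocol gives neither. The sample size of 356 and the power statements in Section 16.3 are unaffected. The conclusion rests only on the wording of the synopsis and Sections 8, 8.1 and 8.2, and assumes nothing about the eligibility form. It should be corrected because the operative rule says the opposite of what the trial intends, not because harm has been shown.

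**What to change.** In Section 8.2 and in the synopsis, either reword the exclusion as *Another likely diagnosis* or move "No other likely diagnosis" to the inclusion criteria. The two are logically equivalent, and both are stricter than requiring autoimmune encephalitis to be the most likely diagnosis. The amendment should therefore reconcile the corrected line with that inclusion item and say explicitly whether a second likely diagnosis bars entry.

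Check the polarity of any matching eligibility item on the trial database, and tell sites how the line is to be read.

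The cost is one line in two places, a sentence of reconciliation and one form check, which can go in with the next amendment. No analysis or sample size text has to change.

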9.1 Participant identification

Potential participants for the study will be identified among hospital inpatients by clinical and laboratory staff, supported by automatic alerts for specific tests, (e.g. requests for anti-neuronal antibodies, Herpes Simplex virus PCR, or other viral CSF PCR). Recruiting hospitals will screen patients with suspected encephalitis for possible recruitment into the study. Once patients have been identified as potentially suitable, eligibility will be confirmed by a clinician listed on the delegation log and recorded in the patient notes.

9.2 Screening logs

A screening log of all potential patients who were screened but found to be ineligible, and those eligible but not consented/not approached as well as the identification pathway will be kept at each site so that any biases from differential recruitment will be detected. Screening activity at sites will be monitored regularly. When at site, logs may contain identifiable information, but this **must** be redacted prior to being sent to the CTR. The screening log should be sent to [contact] every month (see section 25 for further detail on data monitoring/quality assurance). Screening activity will be reviewed regularly at the TMG along with the different stop/Go decision time points to ensure that recruitment is on target.

9.3 Informed consent

Due to the nature of the condition (autoimmune encephalitis) eligible patients may lack capacity to provide informed consent. Encephalitis is characterised by a progressive decrease in the level of consciousness and altered cognition, and memory, especially retention of new information, may be impaired early in the clinical course (Lancaster 2016). Consent procedures will be conducted in accordance with the Mental Capacity Act 2005 and, as it is a Clinical Trial of a Medicinal Product

(CTIMP), with the Medicines for Human Use (Clinical Trial) Regulations 2004 and the incoming Clinical Trials Regulations 536/2014.

As detailed below, consent procedures will differ according to the mental capacity of the patient. Informed consent must be obtained from the patient or a legal representative prior to any trial procedures being undertaken. It will also be necessary to collect contact details for friend or relative who will act as a study partner for the participant. This will facilitate data collection once the participant has been discharged from hospital. A participants' study partner may be asked to complete questionnaires on behalf of the patient, if the participant is unable.

The following information sheets apply:

Participant

- Participant Information Sheet
- Participant Consent Form
- Recovered Capacity Participant Information Sheet
- Recovered Capacity Participant Consent Form
- Pictorial Participant Information Sheet

Legal Representative (Personal or Professional)

- Legal Representative Information Sheet
- Legal Representative Consent Form

Study Partner

- Study Partner Information Sheet
- Study Partner Consent Form

Mental Capacity Assessment: According to the principles of the Mental Capacity Act, potential participants will be assumed to have capacity unless it is established that they lack capacity. A person who 'lacks capacity' means a person who lacks capacity to make a particular decision or take a particular action for themselves at the time the decision or action needs to be taken.

Where there is a concern that a potential participant lacks capacity to provide informed consent for themselves to participate in the trial, they will be assessed for mental capacity by delegated individuals (e.g. recruiting clinician) according to the Mental Capacity Act 2005, which provides a legal framework within which health and care professionals must act. To help determine if a person lacks capacity to make particular decisions, the Mental Capacity Act sets out a two-stage statutory test of capacity. The Mental Capacity Code of Practice provides comprehensive advice on good practice for the assessment of capacity, which is time and decision specific.

A standard template for recording of the mental capacity assessment will be provided to participating sites, together with specific training on the use of this template. This document will be reviewed by a delegated individual (e.g. recruiting clinician) to enable a decision to be made regarding the mental capacity of the potential participant, prior to seeking consent. The mental capacity assessment and outcome will be documented using the template provided.

Consent will be sought from potential participants able to provide informed consent. Where a potential participant is assessed as lacking capacity to consent to the trial, informed consent will be sought from their legal representative (see below).

Participant informed consent: Consent may be taken by the local Principal Investigator or a trained member of the study team delegated to do so. The potential participant will be provided with information about the trial via the Participant Information Sheet (PIS).

The participant will be given sufficient time after the initial invitation to participate, and the opportunity to ask questions, before being asked to sign the Consent Form. Informed consent will be obtained prior to the participant undergoing procedures that are specifically for the purposes of the trial. One copy of the signed Consent Form to be given to the participant, and the original copy to be kept in the investigator site file and a further copy to be kept with participant's hospital notes.

The right of the participant to refuse to participate in the trial without giving reasons must be respected. Similarly, the participant remains free to withdraw at any time from the protocol treatment or any trial activity, including use of samples, without giving reasons and without prejudicing his/her further treatment.

Participants lacking capacity: Where a potential participant lacks capacity to provide consent for themselves, in accordance with the Medicines for Human Use (Clinical Trial) Regulations 2004, a legal representative will be identified and approached to provide consent. The legal representative is someone who 'by virtue of their relationship' with the potential participant, is suitable to act as their legal representative for the purposes of the trial and is available and willing to act as a legal representative. This will usually be a friend or relative, who acts as a Personal Legal Representative (PerLR). In the unusual circumstance that no friend or relative can be identified, or there is insufficient opportunity to identify and approach such a person, a doctor or other health care worker who is not connected to the study will be approached to act as a Professional Legal Representative (PrLR).

Legal representative consent (PerLR and PrLR): The legal representative will be provided with information about the trial and the Legal Representative Information Sheet. They will be asked to consider what the person's views would have been regarding inclusion in the research if they had

capacity to make the decision for themselves, and will be asked to provide informed consent on their behalf that represents the person's 'presumed will'. The legal representative should be given sufficient time after the initial invitation, and an opportunity to ask questions, before being asked to sign the Legal Representative Consent Form.

Participants regaining or losing capacity during the trial: Mental capacity is subject to fluctuations, and participants who lack capacity to consent at the time of enrolment may regain capacity during the trial. Appropriate trial personnel (clinicians, Research Nurses) will conduct ongoing assessment of participants' capacity during data collection and trial assessment visits. If a participant who was initially assessed as lacking capacity, regains capacity during the trial period, the participant will be fully informed about the trial and provided with Recovered Capacity Participant Information Sheet, and informed consent to remain in the trial will be sought from the participant and documented on the Recovered Capacity Participant Consent Form.

If there are concerns about the capacity of a participant who provided consent at the time of enrolment, a capacity assessment may be required. Whilst the participant's informed consent for the trial will remain valid under the Medicines for Human Use (Clinical Trial) Regulations 2004, the involvement of a Legal Representative should be sought in order to advise regarding any future withdrawal from the trial.

Study Partner: Due to the nature of the condition it may be necessary to ask the patient's friend or a family member to complete some of the questionnaires on their behalf. The friend or family member will be approached at the same time that the participant will be approached. The friend or family member will be provided with information about the trial and their role in the trial (i.e. Study Partner Information Sheet (SPIS). The detailed SPIS will include: the exact nature of the trial; what it will involve for the participant and the patient's friend or relative, the implications and constraints of the protocol; and any risks involved in taking part. They will be given sufficient time to review the information sheet and ask any necessary questions. Participants with capacity will also be asked to confirm they are happy for the friend or a family member to answer any necessary trial questionnaires on their behalf if they are unable to do so. If the family member or friend is also the legal representative we will ask them to sign the study partner consent form as well.

9.4 Registration and Randomisation

9.4.1 Registration

Once patients are identified and deemed eligible via the screening procedure, informed consent is taken either from the participant themselves or a legal representative (see section 9.3 for details), and participant's study partner will provide consent for their contact details to be stored. Consent and eligibility will then be confirmed on the trial database for participant registration. On registration, all participants will be assigned a unique identification number. All screening procedures are part of standard of care, and no protocol-required evaluations will be conducted until after informed consent is obtained.

9.4.2 Randomisation

Following confirmation of consent, sites will complete of the baseline assessments. Participants will then be individually randomised to either receive IVIG or placebo. Patients will be randomised 1:1 to IVIG or placebo using random permuted blocks stratified by site, and time from symptom onset. The final randomisation lists, which will contain investigational medicinal product identifications and corresponding allocations (IVIG / placebo), will be generated by a statistician otherwise not involved in the trial and will be supplied to the manufacturing and site pharmacy for appropriate labelling, as well as the CTR safety team. Randomisation will take place online using Vanilla, a system created by the Cardiff University Centre for Trials Research. It will be available 24 hours a day. On randomisation, a participant will be allocated to the next available treatment. The research team, treating healthcare professionals, participants and their families will remain blind to allocated treatment for the duration of the study.

In the instance that the online randomisation system is not working, sites will contact the trial team by emailing the trial inbox ([contact]). The trial team will then let sites know when the system is functioning again. Sites will be informed in advanced of any scheduled downtime in the servers that would prevent them from using the system. If necessary, randomisation may be performed by CTR staff using hardcopy lists.

10 Withdrawal & lost to follow-up

10.1 Withdrawal

Although the IMP in this trial is used in the patient population for this indication, its use is in addition to current standard practice but poses minimal risk to the participant. The treating clinician will retain

oversight on whether or not to adhere to the protocol treatment plan. Participants have the right to withdraw consent for use of clinical data collected in any aspect of the trial at any time. The participants' care will not be affected at any time by declining to participate or withdrawing from the trial. Some participants may wish to withdraw the use of the data upon first approach for deferred consent, following treatment with the IMP. For both participants who provides deferred consent and those who provide consent from the outset but then subsequently request to withdraw from the trial, clear distinction must be made as to what aspect of the trial the participant is withdrawing from. These aspects could be:

- i. Withdrawal from regular GOSE assessments (fortnightly or monthly) but still attend 3
 month, 12 month or annual follow up assessments.
- ii. Withdrawal from completing questionnaires or attending clinical assessments
- iii. Partial withdrawal from Sample collection
- iv. Complete withdrawal from further data collection
- v. Withdrawal of permission to use data already collected

The withdrawal of participant consent shall not affect the trial activities already carried out and the use of data collected prior to participant withdrawal, unless participants withdraw consent to use data that has already been collected.

Participants who consent and subsequently withdraw are invited to complete a withdrawal form (see Withdrawal Form in trial pack). If they decline, the withdrawal form should be completed by the researcher/clinician based on information provided by the participant. The information from the withdrawal form should also be recorded in the patient's medical notes. This withdrawal form should be sent to the trial inbox ([contact]). Any queries relating to potential withdrawal of a participant should be forwarded to the trial inbox ([contact]).

It is important to collect safety data ongoing at the time of withdrawal, especially if the participant withdraws because of a safety event. If a participant wishes to stop taking part in the trial completely, they will need to be seen one last time for an assessment and tests. If the participant is suffering a serious reaction to the trial treatment when they decide to stop, you will need to continue to collect information about them for as long as the reaction lasts. At time of registration, consent for collecting data relating to a serious reaction after a participant withdraws from the trial will be collected. This information is contained in the participant information sheet.

